4.2.5.2 Sensitivity analyses

Controlled imputation

Sensitivity analyses of the repeated measures analyses will be performed for all 4 of the continuous key secondary endpoints using controlled sequential multiple imputation methods based on pattern mixture models. The multiple imputations will be done in 2 steps:

- i. The non-monotone (intermediate visits) missing values will be imputed first, assuming MAR (the Markov chain Monte Carlo [MCMC] method will be used to partially impute the data using SAS PROC MI).
- ii. Then, the remaining monotone missing values at each visit will be imputed using the sequential regression method (using the MONOTONE REG option in PROC MI). At each iteration, missing values will be imputed sequentially, one time-point at a time.

Different assumptions will be made to impute the monotone missing data:

- a. MAR: Missing data in each arm will be imputed assuming the distribution within that treatment group.
- b. MNAR/DRMI: Missing data will be imputed differently depending on the reason for study withdrawal.

Missing data for subjects in the tezepelumab arm who dropped out for a treatment-related reason will be imputed assuming the subject's whole distribution, both pre-withdrawal and post-withdrawal, is the same as the placebo arm (the "copy reference" approach), whereas the remaining subjects will be imputed assuming MAR.

Subjects with missing baseline data will be excluded from these analyses.

Table 7 summarises how tezepelumab subjects withdrawing from study will be handled in the DRMI analyses described above.

Step(a):

In Step (i) above, a single Markov chain will be used with a non-informative (Jeffreys) prior distribution. The first 200 iterations will be discarded to allow for convergence to a stationary distribution and to remove the effect of the starting values ("burn-in"). A gap of 100 iterations will be used between imputations to ensure independence between imputations ("thinning"). Convergence of the MCMC algorithm will be assessed. Non-monotone missing data are expected to be relatively infrequent.

Step(b):

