The sequential monotone regression method in Step (ii) is achieved by only including selected data at each stage of the imputation. This is implemented as follows, where t represents each post-baseline visit, proceeding one visit at a time from the first post-baseline visit until the imputed dataset has complete values at all post-baseline visits. If a negative value is imputed at any time, it will be replaced with a zero value.

MNAR/DRMI

To impute missing values at time t for subjects in the tezepelumab arm who withdrew from the study for treatment-related reasons, the imputation model will use only placebo subjects who had observed data at time t ; the dataset itself also needs to include the tezepelumab subjects who withdrew for treatment-related reasons at time $t-1$, since it is these subjects for which the imputation is required.

To impute missing values at time t for all placebo subjects and tezepelumab subjects who withdrew from the study for reasons unrelated to treatment, the imputations are performed assuming MAR i.e. using an imputation model which uses subjects who had observed data at time t from within the respective treatment group. If a negative value is imputed at time t , then it will be replaced with a zero value.

For each of the MAR and DRMI analyses, 100 imputations will be carried out. A random seed of 670376 will be used for the non-monotone imputations, and a random seed of 966654 will

be used for the monotone imputations. These same random seeds will be used for the multiple imputation analyses of all 4 key secondary endpoints.

The imputation models will use absolute values of the relevant endpoint (including the baseline value). Change from baseline will then be calculated in imputed datasets. The imputation model will include the same baseline covariates as used in the main analysis model (i.e. those specified in [Section 4.2.5.1](#)).

Each of the imputed datasets will be analysed using the same MMRM model specified in [Section 4.2.5.1](#). The results from the analysis on each imputed dataset will be combined across imputations in a way which appropriately accounts for within-imputation and between-imputation variance (using the SAS procedure PROC MIANALYZE).

Tipping point analysis

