A tipping point analysis will be performed for each of the four continuous key secondary endpoints, using similar multiple imputation methodology. In this analysis, various degrees of improvement in the placebo group δ_P after withdrawal, and various degrees of worsening in the tezepelumab group δ_T after withdrawal, will be simultaneously explored.

Placebo subjects who withdrew from the study (irrespective of reason for discontinuing IP) will have their first imputed value improved by δ_P . This results in a one-time shift towards a better value in the outcomes of placebo subjects that withdrew from the study after a given visit. Tezepelumab subjects who withdrew from the study (irrespective of reason for discontinuing IP) will have their first imputed value worsened by δ_T . This results in a one-time shift towards a worse value in the outcomes of tezepelumab subjects that withdrew from the study after a given visit.

Tipping points are defined as the range of smallest values (δ_P, δ_T) which would result in a change of conclusion, the latter being assessed according to the nominal statistical significance levels applied in [Section 4.1.2](#).

Step (i) will first be applied to the non-monotone missing values, exactly as specified above for control imputation.

For step (ii), the sequential monotone regression method will also be applied. To impute missing values at time t for subjects in the placebo arm, an imputation model which uses placebo subjects who had observed data at time t will be used, and the one-time improvement δ_P applied to this. To impute missing values at time t for subjects in the tezepelumab arm, an imputation model which uses tezepelumab subjects who had observed data at time t will be used, and the one-time worsening δ_T applied to this. In other words, imputation will be performed within each treatment arm, and therefore $(\delta_P, \delta_T) = (0, 0)$ corresponds to the MAR analysis.

For pre-BD FEV₁ change from baseline:

- δ_P will be varied from 0 to 0.3 L in increments of 0.1 L
- δ_T will be varied from 0 to -0.3 L in increments of 0.1 L.

If a tipping point was observed with analysis using 0.1 mL increments, smaller increments of 0.05 mL will then be explored in the relevant range to determine the tipping point more precisely.

For AQLQ(S)+12 total score change from baseline:

- δ_P will be varied from 0 to 3 in increments of 1
- δ_T will be varied from 0 to -3 in increments of 1.

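### The key secondary tipping-point analysis shifts only the first imputed visit, so its nominal deltas overstate the departure from MAR at Week 52, where the conclusion is judged

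*SAP*

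**What the plan says.** SAP 4.2.5.2, Tipping point analysis, covers pre-BD FEV1, AQLQ(S)+12, ACQ-6 and weekly mean ASD. Placebo subjects who withdraw from the study "will have their first imputed value improved by δ_P". Tezepelumab subjects who withdraw "will have their first imputed value worsened by δ_T". The SAP describes this openly: "This results in a one-time shift towards a worse value in the outcomes of tezepelumab subjects".

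The remaining monotone missing visits are filled by sequential regression: "At each iteration, missing values will be imputed sequentially, one time-point at a time". For the active arm, "an imputation model which uses tezepelumab subjects who had observed data at time t will be used", and the placebo arm is handled in the same way. Completed data go to the main model: "Each of the imputed datasets will be analysed using the same MMRM model specified in" Section 4.2.5.1. The hypotheses in SAP 4.1.1 concern Week 52 only. "Tipping points are defined as the range of smallest values" of the two deltas that change the conclusion at the nominal levels of SAP 4.1.2.

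The grids run, per arm and in opposite directions, to 0.3 L (FEV1), 3 points (AQLQ and ACQ-6) and 2 points (ASD). No delta is added at later visits, and the SAP does not ask for the resulting Week 52 shift to be reported.

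**The concern.** A tipping-point result is read as a statement about how bad the unobserved outcomes would have to be before the claim fails. Here the unobserved outcome that matters is the Week 52 value, but delta is put on the first missed visit. At each later visit the shifted value is one predictor among baseline and all earlier visits, with coefficients estimated from unshifted own-arm data. The imputed path therefore drifts back towards the arm's usual course, and the reported pair (δP, δT) is larger than the Week 52 departure that was tested.

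The primary-endpoint tipping point (SAP 4.2.4.2) works differently. Its factors multiply the exacerbation rate used to impute the missing post-withdrawal data, so the departure lasts to the end of the planned treatment period. Two analyses with the same name would be read alike although one is sustained and the other fades.

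At stake is what may be said about the robustness of the confirmatory claims at Levels 3 to 5. The main MMRM tests and Type 1 error control are not affected.

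**Working it through.** **Inputs from the documents.** 530 per arm, 2-sided 5%, SD 400 mL and 1.3 units, planned differences 100 mL and 0.3 units (SAP 1.3). Dropout of 10%, uniform, is stated there for the primary endpoint and borrowed here. Post-baseline time points (Protocol Table 2): FEV1 at Weeks 2, 4, 8, 12, 16, 24, 36, 52; AQLQ at Weeks 4, 12, 24, 36, 52; ACQ-6 at 14 visits. ASD has 52 weekly means (SAP 4.2.5.1).

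**Assumed.** Between-visit correlations: compound symmetry 0.5, 0.7, 0.9; AR(1) 0.8, 0.9, 0.95, 0.98 per 4 weeks; and two mixtures of a stable subject component (0.5 or 0.3 of the variance), an AR(1) 0.9 component (0.3 or 0.5) and noise (0.2).

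**Step 1, the plan's own figures.** Critical difference = 1.96 × SD × √(2/530). FEV1: 1.96 × 24.57 = 48.2 mL. Scores: 1.96 × 0.0799 = 0.157. The SAP gives 50 mL and 0.16. Power is 98.3% and 96.4%, against the stated 95% or higher. The figures reproduce.

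**Step 2, share of delta reaching Week 52.** Put 1 on the first missed visit s and 0 on earlier visits. For each later visit t, the carried shift is the sum over earlier visits of (regression coefficient of t on that visit) × (shift there). The value at Week 52 is f(s). The average is f = Σ f(s) × (weeks between s and the preceding visit)/52.

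Example: under compound symmetry 0.5, a subject first missing FEV1 at Week 36 has 8 predictors of Week 52 (baseline and seven visits). Each has coefficient 0.5/(1 + 7 × 0.5) = 0.11, so 11% of delta arrives. A subject first missing at Week 52 keeps all of it.

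**Step 3, what is needed to tip.** The treatment difference moves by 0.10 × f × (δP + |δT|). The move needed is 100 − 48.2 = 51.8 mL, or 0.300 − 0.157 = 0.143 units. Dividing by 0.10 gives a total Week 52 delta of 0.518 L or 1.43 units. Dividing that by the largest grid total gives the smallest f that tips inside the grid.

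| Endpoint | First missing at Week 52 | f, range | Largest δP + \|δT\| | Smallest f that tips | Structures that tip |
|---|---|---|---|---|---|
| FEV1 | 16/52 = 31% | 0.41–0.90 | 0.6 L | 0.86 | 1 of 9 |
| AQLQ | 16/52 = 31% | 0.46–0.91 | 6 | 0.24 | 9 of 9 |
| ACQ-6 | 4/52 = 8% | 0.19–0.89 | 6 | 0.24 | 6 of 9 |
| ASD | 1/52 = 2% | 0.08–0.88 | 4 | 0.36 | 3 of 9 |

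With the full delta at Week 52 (f = 1), all four tip at the corner. The lowest f for every endpoint comes from compound symmetry. The highest comes from AR(1) 0.98 per 4 weeks without measurement noise. FEV1 tips only there. For AQLQ the nominal delta exceeds the Week 52 delta by 1/0.91 = 1.1 to 1/0.46 = 2.2 times.

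**Step 4, check by simulation.** 530 per arm, 10% uniform dropout, sequential regression with 15 imputations, a baseline-adjusted Week 52 comparison, Rubin's rules and 80 replicates, under compound symmetry 0.7 and one mixture. ASD was not simulated here.

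| Grid point | As written | Full delta at Week 52 |
|---|---|---|
| FEV1, 0.3 / −0.3 L | 69–72 mL, significant in 84–90% | 37–40 mL, 34–36% |
| AQLQ, 1 / −1 | 0.18–0.20, 66–73% | 0.09–0.10, 19–25% |
| ACQ-6, −2 / 2 | −0.16 to −0.22, 59–84% | +0.10, 0% |

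**The case against.** The strongest reply is that this is a disclosed and coherent missing-not-at-random assumption: a step change at withdrawal, after which the subject evolves like own-arm subjects with the same history. Nothing in the documents requires a sustained shift. The reason-based copy-reference imputation in the same section is a second MNAR check. This stands. The point concerns how the deltas will be read, and no passage contradicts another.

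The grids are also wide and move both arms apart. Even at the lowest share, the between-arm Week 52 departure among withdrawn subjects at the corner is 0.41 × 0.6 = 0.25 L for FEV1, against a planned 0.1 L. It is 0.46 × 6 = 2.8 for AQLQ and 0.19 × 6 = 1.1 for ACQ-6, against 0.3. Not tipping there would still mean something. Only ASD (0.08 × 4 = 0.32) becomes weak, and only under some structures.

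The FEV1 contrast is narrow. With full delta at Week 52, only one of the 16 initial grid points tips: (0.3, 0.2) gives 0.10 × 0.5 = 0.050 L, just short of 0.052 L. Heavier dropout changes the answer: at 20% the smallest f needed falls to 51.8/(0.20 × 600) = 0.43.

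Three stronger readings are tempting and not supported:

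- A reader might infer that delta never reaches Week 52. Part of it does in every structure, and subjects first missing at Week 52 carry it whole.
- A reader might infer that the results are bound to look robust. AQLQ tips inside its grid in all nine structures, and ACQ-6 in six.
- A reader might infer that the zero floor ("If a negative value is imputed at any time, it will be replaced with a zero value") adds to the bias by limiting placebo improvement on ACQ-6 and ASD. That rule is written under controlled imputation. The tipping-point text carries over only the non-monotone step exactly, so flooring after delta is an inference. Uncapped worsening in the active arm would also make tipping easier.

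**Conclusion.** The point holds as a weakness of interpretation. In every structure tried, the average share of delta reaching Week 52 was below 1, so the error is always towards apparent robustness. Its size is uncertain because it depends on correlations and dropout timing that the documents do not give. It can be large for ASD and ACQ-6, which are measured most often.

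With the planned effects and 10% uniform withdrawal, the one-time shift can remove the FEV1 tip at the grid corner, often the ASD tip, and the ACQ-6 tip under compound symmetry. The calculation uses the nominal 5% level and the complete-data standard error. The truncated Hochberg levels and the variance added by imputation would move the thresholds somewhat. With 80 replicates, the simulated percentages carry a standard error of up to about 5 points.

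The change should be made, because it determines what the robustness analysis is entitled to conclude.

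**What to change.** In SAP 4.2.5.2, Tipping point analysis:

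1. Keep the one-time shift if it is wanted, described as a transient departure at the first missed visit.
2. Add a sustained version. Complete the within-arm MAR monotone imputation first, then add δP or δT to every imputed post-withdrawal value of each withdrawn subject (or to the imputed Week 52 value), refit the MMRM and combine. This brings the key secondary analysis closer to the primary-endpoint tipping point.
3. For both versions, report beside each nominal (δP, δT) the implied mean shift at Week 52 among withdrawn subjects, by arm, relative to the MAR imputation.

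The cost is a paragraph of SAP text, one data step on imputations already planned, and extra model fits. The robustness statement may become less favourable, most likely for FEV1 and ASD.

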4.2.5.3 Supplementary analyses

The MAR analyses specified in [Section 4.2.5.1](#) will be repeated using on-treatment data only, where the definition of on-treatment is given in [Section 2.1.5](#).

4.2.5.4 Supporting analyses

As a supportive analysis to the analysis of change from baseline in ACQ-6, the main ACQ-6 analysis described in [Section 4.2.5.1](#) will be repeated for change from baseline in ACQ-5 and ACQ-7 score using a similar MMRM model. Similar descriptive and graphical summaries will also be produced.

The analysis of AQLQ(S)+12 total score change from baseline will be repeated for change from baseline in each of the 4 AQLQ(S)+12 domain scores using a similar MMRM model.

The analysis of ACQ-6 score change from baseline will be repeated for change from baseline in each of the 6 individual ACQ-6 items using a similar MMRM model.

As further supportive analyses to the analyses of change from baseline in ACQ-6, AQLQ(S)+12 and weekly mean ASD, responders/non-responders will be summarised descriptively and analysed using a generalised linear model for repeated measures, using a logit link function. The response variable in the model will be the binary responder status at each scheduled post-randomisation visit up to and including Week 52, irrespective of whether the subject remained on treatment and/or took other treatments. Treatment, visit, region, age (adolescents or adults) and treatment by visit interaction will be included as factors in this model. Baseline of the corresponding endpoint will also be included in the model as a continuous linear covariate.

In this model, inference will be based on generalised estimating equations (GEEs) using the method of [Liang and Zeger \(1986\)](#). An unstructured working correlation matrix will be used, along with empirically corrected standard errors. For the ASD responder endpoint, each of the 52 weeks used for weekly mean calculation will replace visit in the above model specification.

Only the first (responder/non-responder) ACQ-6 and AQLQ(S)+12 definitions in [Section 3.2.3.3](#) will be analysed using the repeated measures GEE analysis. The other categorical definitions in this section will be summarised descriptively only.

Change from baseline in the percentage of asthma symptomatic days (as defined in [Section 3.2.3.5](#)) will be summarised for the on-study period for each post-baseline week using descriptive statistics.

As further supportive analysis to the analysis of change from baseline in weekly mean total (daily) ASD score, the main ASD analysis described in [Section 4.2.5.1](#) will be repeated for changes from baseline in weekly mean daytime and night-time ASD scores using a similar MMRM model. Similar descriptive summaries will also be produced.

As further supportive analysis to the analysis of change from baseline in weekly mean total (daily) ASD score, the main ASD analysis described in [Section 4.2.5.1](#) will be repeated for changes from baseline in weekly mean ASD individual symptom scores (see [Section 3.2.3.6](#)) using a similar MMRM model. Similar descriptive summaries will also be produced.

4.2.5.5 Assessing efficacy across phenotypes and other baseline characteristics

Efficacy for the key secondary endpoints will be evaluated separately for biomarkers of interest (which comprises an evaluation of both categorical subgroups and the continuous biomarker variable), and other exploratory variables (which comprises an evaluation of categorical subgroups only).

The same variables will be evaluated for consistency of effect for each of the 4 key secondary endpoints (changes from baseline to Week 52 for each of pre-bronchodilator FEV₁, AQLQ(S)+12 total score, ACQ-6 score and weekly mean ASD score).

Descriptive summaries of the key secondary endpoints will be presented for the specified categorical variables below, irrespective of how few subjects there are in any particular subgroups. For model-based analyses, if any of the subgroups have fewer than 10 subjects in one or both treatment groups (with data at any post-baseline time point, not necessarily at Week 52), this subgroup level will not be included in the model. If that leaves only one subgroup level, the model will not be fitted for that categorical variable. If it leaves more than one subgroup level, the model will be fitted using the remaining subgroups which have 10 or more subjects in both treatment groups.

Biomarkers of interest

Descriptive summaries of each of the key secondary endpoints by treatment group will be produced for each of the following categorical variables:

- Baseline eosinophils group: $<300/\mu\text{L}$, $\geq 300/\mu\text{L}$
- Baseline eosinophils group: $<150/\mu\text{L}$, $150-<300/\mu\text{L}$, $300-<450/\mu\text{L}$, $\geq 450/\mu\text{L}$
- Baseline eosinophils group: $<150/\mu\text{L}$, $\geq 150/\mu\text{L}$
- Baseline clinic visit FENO group: $<25\text{ppb}$, $\geq 25\text{ppb}$
- Baseline clinic visit FENO group: $<25\text{ppb}$, $25-<50\text{ppb}$, $\geq 50\text{ppb}$
- Baseline perennial specific IgE status (FEIA): Any perennial FEIA positive, All perennial FEIA negative, Unknown perennial FEIA

A similar MMRM model will be fitted as for the key secondary endpoints for each of the above variables in turn, with additional factors for the subgroup variable and the treatment by visit by subgroup interaction (as well as lower order interaction terms including these factors). This model will be used to estimate the treatment effect and its 95% CI within each of the subgroup categories at Week 52, which will be tabulated and also summarised graphically using a forest plot. The overall treatment effect at Week 52 will be displayed on the forest plot.

For the ASD endpoint, each of the 52 weeks used for weekly mean calculation will replace visit in the above model specification.

A p-value for the treatment by subgroup interaction at Week 52 will not be presented for each of these models due to the various difficulties in interpretation.

For the FEV₁ endpoint only, adjusted means from the above model will additionally be summarised graphically over time and used to evaluate time of onset of effect within each biomarker subgroup category (baseline eosinophils $<300/\mu\text{L}$, $\geq 300/\mu\text{L}$; baseline clinic visit

FENO group: <25ppb, ≥25ppb; baseline perennial specific IgE status (FEIA): Any perennial FEIA positive, All perennial FEIA negative, Unknown perennial FEIA).

Standardised effect plots will be produced for each of the key secondary endpoints, similar to what was described in [Section 4.2.4.5](#).

Any unexpected observed pattern may also be further explored using resampling techniques, where null hypothesis data will be generated (in many iterations) to assess the probability of seeing a pattern as strong (or stronger) by chance only; the null hypothesis will correspond to keeping the main effects intact whilst breaking any potential predictive property of the biomarkers.

A LOESS plot will be produced for each of the continuous biomarker variables (baseline eosinophils (cells/μL), baseline FENO (ppb) and baseline total serum IgE (IU/mL)), for each of the key secondary endpoints.

The categorical subgroup analysis above will also be repeated, for each of the key secondary endpoints, using the four (mutually exclusive) categories defined by the quartiles of each baseline biomarker.

Other exploratory variables

Descriptive summaries of each of the key secondary endpoints by treatment group will be produced for each of the following categorical variables:

- ICS dose at study entry: medium, high
- Age category: adults (≥65), adults (≥18 to <65) and adolescents (≥12 to <18)
- Gender: Male, Female
- Race: White, Black or African American, Asian, Other
- Exacerbations in the year before study: ≤2 exacerbations, >2 exacerbations
- OCS at baseline: present, absent
- Baseline body mass index (BMI): <18.5 kg/m², 18.5-<25.0 kg/m², 25.0-<30.0 kg/m², ≥30.0 kg/m²
- Geographical region: Asia Pacific, North America, South America, Central/Eastern Europe, Western Europe plus Australia, Rest of World
- Nasal polyps in the 2 years before randomisation status: Yes, No

A similar MMRM model will be fitted as for the key secondary endpoints for each of the above variables in turn, with additional factors for the subgroup variable (where not already included) and the treatment by visit by subgroup interaction (as well as lower order interaction terms including these factors). This model will be used to estimate the treatment effect and its 95% CI within each of the subgroup categories at Week 52, which will be tabulated and also summarised graphically using a forest plot. The overall treatment effect at Week 52 will be displayed on the forest plot.

For the ASD endpoint, each of the 52 weeks used for weekly mean calculation will replace visit in the above model specification.

For age, the above categorisation will replace the one used in the main analysis models for the key secondary endpoints.

A p-value for the treatment by subgroup interaction at Week 52 will not be presented for each of these models due to the various difficulties in interpretation.

Standardised effect plots will be produced separately for:

- Subgroups defined using pre-specified categories (biomarkers of interest and other exploratory variables on the same plot)
- Subgroups defined using quartiles of the baseline data (biomarkers of interest only).

